5.2. Analysis methods

The effects on primary and secondary outcomes in response to the present 12-week intervention will be assessed based on repeated-measures linear mixed-effects multilevel models. Individual measures of change will be therefore modeled as a function of the randomly assigned group, assessment time, and their interaction terms. All the analyses will also be conducted separately for men and women. Model-based estimations will be performed with an intention-to-treat approach (primary analyses) using the restricted maximum-likelihood method, the model assuming that missing values are missing-at-random. Analyses and estimations will also be performed with a per-protocol approach, and an attrition propensity will be calculated using a logistic model predicting attrition with baseline values of allocation group, age, sex, and BMI. Additional models will be conducted including energy intake, physical activity, or reproductive status in women. In addition to the conventional approach of assessing intervention effects

based on statistical and practical significance, it is important to highlight that this study will employ a practical benefit approach. This approach emphasizes the reporting of unadjusted values that are intuitive to human judgment and easily replicable, considering the design and methodology of the study.

The main statistical analyses will be performed by an independent researcher ([name]), who is not involved in the recruitment, evaluations, and interventions, and will be performed blinded to the treatment allocation by coding the intervention arms (e.g., A, B, C, D).

5.3. Missing data

The number of missing data will be reported, and patterns of missing data will be explored. Based on previous experience, we expect that missing data will be assumed as missing at random. Therefore, the linear mixed model analyses will handle our missing data. However, once the data processing is finalized, we will reconsider this assumption. In case we believe this assumption does not hold, we will take appropriate measures for the data analyses by using, for example, other multiple imputation techniques.

5.4. Additional analyses

Changes in other outcomes will be analysed using a similar protocol as described by ‘5.2 Analysis methods’ unless other analyses would be more appropriate depending on the outcome (e.g., ordinal / dichotomous outcomes). Furthermore, cross-sectional analyses will be performed using the baseline data of the RCT. For example, cross-sectional associations will be explored by bivariate and partial correlations. Then, further analyses will be performed using linear and logistic regression depending on the nature of the study variables and research questions. ANOVAs will also be used to test differences in outcomes among groups.

5.5. Harms

The number and reasons of adverse events (e.g., headache, dizziness, falls, injuries, musculoskeletal problems, cardiovascular disease events, and any other events potentially related to the implementation of the trial protocol) at each time point will be collected, reported, and described separately for each study arm. No formal statistical testing will be undertaken.

5.6. Statistical software

The analyses will be performed using R. For the main analyses we will use the ‘lme4’ or ‘LMMstar’ package. The use of packages will be reported in the manuscript.

[figure not shown]
6. References

2. Ezpeleta M, Gabel K, Cienfuegos S, et al. Effect of alternate day fasting combined with

aerobic exercise on non-alcoholic fatty liver disease: A randomized controlled trial. *Cell Metab.* 2023;35(1):56-70.e3. doi:10.1016/j.cmet.2022.12.001

TEMPUS

Statistical Analysis Plan

University of Granada, Spain

Trial registration number: NCT05897073

Version: 2

Date: 01/07/2024

Statistical analysis plan (SAP) revision history: revision made on 1st, July, 2024

Roles and responsibility:

Name and address of principal investigator and trial coordinators:

[name]. [name] (principal investigator)
[name] (trial coordinator)
[name] (trial coordinator)
PROFITH (PROmoting FITness and Health Through Physical Activity) research group, Department of Physical Education and Sports, Sport and Health University Research Institute (iMUDS), University of Granada
Faculty of Sport Sciences, [name]

Name of person writing SAP:

E-mail principal investigator: [contact]
E-mails trial coordinators: [contact] & [contact]
PROFITH research group, Department of Physical Education and Sports, Faculty of Sport Sciences, Sport and Health University Research Institute (iMUDS), University of Granada, Granada, Spain

Signatures:

[name]. [name] (principal investigator)

Date: 01/07/2024

[name] (trial coordinator)

Date: 01/07/2024

[name] (trial coordinator)

Date: 01/07/2024

Table of contents

1. General information of TEMPUS study	17
1.1. Background and rationale	17

1.1. Background and rationale

Metabolic dysfunction-associated steatotic liver disease (MASLD) is a major public health concern due to its high prevalence and strong association with extrahepatic conditions, particularly among adults with obesity, in whom it often remains undiagnosed. Emerging approaches such as time-restricted eating (TRE)—a novel form of intermittent fasting—and supervised exercise may represent promising strategies to mitigate associated health risks. Preliminary evidence suggests that combining TRE and exercise may be an effective strategy for improving body composition and cardiometabolic health in adults with obesity. However, studies examining the combined effects of TRE and exercise in humans are scarce and have notable limitations.

1.2. Objective

The overall objective is to investigate the effects of TRE combined with supervised exercise on hepatic fat content (primary outcome) and cardiometabolic health (secondary outcomes) in adults with obesity.

The primary objective is to investigate the effects of a 12-week TRE intervention combined with a supervised exercise intervention (TRE + Exercise), as compared with TRE (TRE) or supervised exercise alone (Exercise), and usual care control group (UC), on hepatic fat content (primary outcome) and cardiometabolic health (secondary outcomes) in adults with obesity.

Secondary aims are to:

- i. Investigate the effects of a 12-week TRE + Exercise intervention, as compared with TRE or supervised exercise alone, and UC, on other specific fat depots: abdominal visceral and subcutaneous adipose tissue, pancreatic fat and mid-thigh intermuscular and intramuscular adipose tissue, and body composition (fat mass and fat-free mass).
- ii. Investigate the effects of a 12-week TRE + Exercise intervention, as compared with TRE or supervised exercise alone, and UC, on cardiometabolic health markers including blood pressure, liver enzymes, glucose homeostasis, blood lipid profile, and circulating inflammatory biomarkers.
- iii. Investigate the effects of a 12-week TRE + Exercise intervention, as compared with TRE or supervised exercise alone, and UC, on fecal microbiota.
- iv. Investigate the effects of a 12-week TRE + Exercise intervention, as compared with TRE or supervised exercise alone, and UC, on sleep and physical activity patterns.
- v. Investigate the effects of a 12-week TRE + Exercise intervention, as compared with TRE or supervised exercise alone, and UC, on psychological outcomes (i.e., depression, stress and anxiety) and quality of life.
- vi. Investigate the effects of a 12-week TRE + Exercise intervention, as compared with TRE or supervised exercise alone, and UC, on physical fitness (i.e., cardiorespiratory fitness and muscular strength).
- vii. Examine the effect of a 12-week TRE + Exercise intervention, as compared with TRE or supervised exercise alone, and UC, on dietary habits and eating behaviour.
- viii. To quantify the persistence of the effects of TRE + Exercise intervention, TRE alone,

and supervised exercise alone on hepatic fat content and cardiometabolic health in the long-term (12-month follow-up).

2. Study methods

2.1. Trial design

The TEMPUS project is an investigator initiated, parallel group, randomized controlled trial (RCT). The RCT will include four-arms containing a UC control group and three intervention groups that will receive three different 12-week TRE and/or supervised exercise programs (**Figure 1**): i) TRE alone, ii) Exercise alone and iii) TRE + Exercise. The study will be conducted in ~184 patients (50% women) with obesity who meet the eligibility criteria. Measurements will be performed at baseline, at midpoint (6 weeks), post intervention (12 weeks) and 12-month follow-up (12 months post intervention). More detailed information is described in the study protocol.¹

The TEMPUS research team will perform the data quality control, data processing, writing analyses scripts/programs and statistical analysis.

[figure not shown]

Figure 1. Overview of the TEMPUS Study. TRE, time-restricted eating.

2.2. Randomization

Participants will be randomized using a parallel design with a 1:1:1:1 allocation ratio and stratified for sex.

2.3. Sample size

Based on previous findings from a recent trial on the combination of alternate day fasting and exercise on hepatic fat content,² we anticipate approximately 5.0% reduction in hepatic fat content in the TRE + Exercise group, 2.5% in the TRE group, 2.5% in the exercise group, and no significant change in this outcome in the usual-care group. Assuming a pre-post correlation of 0.8 and a standard deviation of 6 points in the main outcome, we estimate a medium effect size of 0.45. To detect this effect size as statistically significant in a one-way ANOVA with $\alpha = 0.05$ and a power of 0.8, a minimum of 19 patients per group is required. Accounting for subgroup analyses based on sex and a maximum dropout rate of 20%, we will aim to recruit ~46 participants for each trial group, resulting in a total sample size of ~184 participants, with ~92 women included.

Our sample size calculations have taken into account subgroup analyses by sex. We have conservatively estimated a maximum dropout rate of approximately 20%. By considering this dropout rate, we have ensured that our study is adequately powered to detect the specified effect size even if there are differential dropout rates between men and women. For example, if men have a dropout rate of 5% and women have a dropout rate of 15%, our study will still have sufficient power to analyse the data separately in men and women.

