4.2. Sample size

Based on previous findings from a recent trial on the combination of alternate day fasting and exercise on hepatic fat content (67), we anticipate approximately 5.0% reduction in hepatic fat content in the TRE + Exercise group, 2.5% in the TRE group, 2.5% in the exercise group, and no significant change in this outcome in the usual-care group. Assuming a pre-post correlation of 0.8 and a standard deviation of 6 points in the main outcome, we estimate a medium effect size of 0.45. To detect this effect size as statistically significant in a one-way ANOVA with $\alpha = 0.05$ and a power of 0.8, a minimum of 19 patients per group is required. Accounting for subgroup analyses based on sex and a maximum dropout rate of 20%, we will aim to recruit ~46 participants for each trial group, resulting in a total sample size of ~184 participants, with ~92 women included. To ensure a balanced representation of both sexes and maintain an adequate sample size, we will implement several strategies:

- Recruitment Process: A specific recruitment process will be utilized to aim for an equal enrollment of men and women. For each woman recruited, we will encourage her to invite one man to participate in the study. This approach has been successfully employed in our previous intervention studies and has proven effective in achieving a balanced sex distribution (68–70).
- Sample size calculations: Our sample size calculations have taken into account subgroup analyses by sex. We have conservatively estimated a maximum dropout rate of approximately 20%. By considering this dropout rate, we have ensured that our study is adequately powered to detect the specified effect size even if there are differential dropout rates between men and women. For example, if men have a dropout rate of 5% and women have a dropout rate of 15%, our study will still have sufficient power to analyze the data separately in men and women.
- Expected dropout rate: While we have conservatively estimated the maximum dropout rate, we anticipate that the actual dropout rate will be relatively lower and similar between both sexes. This expectation is based on our previous studies and the measures we have to promote participant engagement and adherence (68–70).

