2.4. Framework

A superiority hypothesis testing framework will be used. In the main analyses, we will compare whether TRE plus exercise interventions (TRE + Exercise group) is superior to TRE or Exercise alone or the UC (Mediterranean education program only).

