3.1. Confidence and P values

All statistical tests will be two-tailed. *P* for significance will be set at 0.05 and 95% confidence intervals will be estimated. No adjustment for multiplicity will be made as multiplicity adjustments may be of lesser importance in the case of distinct treatment arms.³ Moreover, only one primary outcome will be defined and other outcomes (i.e., secondary outcomes, and exploratory analyses) will not require adjustment for multiple testing. However, we will include a hierarchical analytic approach for the interventions tested and the primary outcome.

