5.2. Analysis methods

The main analyses will consist of the intention-to-treat analyses for the primary and secondary outcomes using a constrained baseline (meaning baseline-adjusted) linear mixed model, which accounts for baseline differences among the study groups. The model will include fixed effects

for time (three levels) and treatment (four levels) as well as the unique participant identifier as a random effect, and sex will be included as a covariate. Model assumptions will be checked. In case we detect model violations, we will take appropriate measures by e.g., conducting data transformations. If the global test of significance indicates between-group differences, pairwise comparisons will be explored. Although no adjustments for multiplicity will be performed, family-wise type 1 error rate on the primary outcome will be retained by using a hierarchical analytic approach. The prespecified hierarchical hypotheses will be tested using the prespecified sequence: TRE + Exercise versus UC, TRE versus UC, Exercise versus UC, TRE + Exercise versus TRE, TRE + Exercise versus Exercise, and TRE versus Exercise. The main statistical analyses will be performed by an independent researcher ([name]), who is not involved in the recruitment, evaluations, and interventions, and will be performed blinded to the treatment allocation by coding the intervention arms (e.g., A, B, C, D).

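### The stated power (0.8 at 19 per group) is for a one-way ANOVA, not for the six-step sequence, whose chance of passing through the combined-versus-single steps is 64–77% at 46 per arm and 44–62% after the maximum 20% dropout

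*SAP*

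**What the plan says.** SAP 2.3 (version 2) assumes "we anticipate approximately 5.0% reduction in hepatic fat content in the TRE + Exercise group", then "2.5% in the TRE group, 2.5% in the exercise group, and no significant change in this outcome in the usual-care group". With SD 6 and a pre-post correlation of 0.8 it derives an effect size of 0.45. For a one-way ANOVA at alpha 0.05 it states "a power of 0.8, a minimum of 19 patients per group is required". That number is then raised to about 46 per arm (about 184 in total) for analyses by sex and at most 20% dropout. Protocol 4.2 carries the same calculation: "a minimum of 19 patients per group is required".

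SAP 2.4 sets the main question: "In the main analyses, we will compare whether TRE plus exercise interventions (TRE + Exercise group) is superior to TRE or Exercise alone", or to usual care (UC).

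SAP 5.2 specifies a constrained-baseline mixed model and a global test. If the global test is positive, ordered pairwise tests follow for the primary outcome: "The prespecified hierarchical hypotheses will be tested using the prespecified sequence: TRE + Exercise versus UC, TRE versus UC, Exercise versus UC". Step 4 is TRE + Exercise versus TRE, step 5 is TRE + Exercise versus Exercise, and step 6 is TRE versus Exercise. SAP 3.1 adds "All statistical tests will be two-tailed" and a 0.05 threshold.

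**The concern.** A significant global test shows only that the four arms differ somewhere. On the plan's own means it is driven by the 5-point gap between the combination and UC. Every contrast at steps 2 to 5 is 2.5 points, half that gap. The two comparisons that ask whether the combination adds to a single component can be declared significant only if steps 2 and 3, also 2.5-point contrasts, succeed first.

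The printed 0.8 therefore describes the gate and not the tests behind it. A reader could take it as the chance that the trial answers the question in SAP 2.4. A sequence that stops before step 5 could then be read as an adequately powered negative on added benefit, although such a stop is a fairly likely result when the planned effects are true.

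**Working it through.** **Inputs (SAP 2.3, 3.1, 5.2).** Reductions 5.0 / 2.5 / 2.5 / 0, read as absolute points on the scale of the SD, with UC taken as 0. SD 6, r = 0.8, two-sided alpha 0.05, four equal arms. Planned 46 per arm; after 20% dropout 46 × 0.8 = 36.8, so 36–37.

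**Residual SD.** Change score: 6 × √(2 × (1 − 0.8)) = 3.79. Baseline-adjusted: 6 × √(1 − 0.8²) = 3.60. The second is nearer to the model in SAP 5.2.

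**Effect size.** The arm means deviate from their average of 2.5 by 2.5, 0, 0 and −2.5. Their SD is √(12.5/4) = 1.768, so f = 1.768/3.795 = 0.466 or 1.768/3.60 = 0.491. The printed 0.45 is close to the change-score value, which supports the absolute-points reading. Exactly 0.45 would imply a residual SD of 1.768/0.45 = 3.93.

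**The plan's own figure.** Noncentral F, four groups, noncentrality f² × N, f = 0.45:
- 14 per group: 78%
- 15 per group (0.2025 × 60 = 12.15): 82%
- 19 per group (0.2025 × 76 = 15.39): 91%

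So 80% power needs 15 per group, and the printed pairing of 0.8 with 19 does not reproduce. Nineteen would fit f = 0.40 at 80%, or f = 0.45 at 90%.

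**One 2.5-point contrast, tested alone.** Noncentral t, noncentrality 2.5/(SD × √(2/n)), pooled error df 4n − 4:
- n = 46: 3.16 (change) or 3.33 (adjusted), power 88% or 91%
- n = 37: 2.83 or 2.99, power 80% or 84%
- n = 36: 2.79 or 2.95, power 79% or 83%

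**The sequence.** Four independent arm means and a pooled variance were simulated, 1,000,000 trials per scenario. The global F had to be significant, then each step significant in the favourable direction, in order. Ranges run from the change-score to the baseline-adjusted SD.

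| Probability of passing through | 46 per arm | 36–37 per arm |
|---|---|---|
| Global F | >99% | >99% |
| Step 1 (combination vs UC) | >99% | >99% |
| Step 2 (TRE vs UC) | 88–91% | 79–84% |
| Step 3 (Exercise vs UC) | 80–85% | 68–75% |
| Step 4 (combination vs TRE) | 70–77% | 52–62% |
| Step 5 (combination vs Exercise) | 64–72% | 44–55% |

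As a rough check, four independent tests at 88% would all succeed with probability 0.88⁴ = 0.60. The simulated 64% differs because the contrasts share arms. The global test costs almost nothing.

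With SD 3.93, steps 4 and 5 fall to 65% and 58% at 46 per arm, 49% and 41% at 37, and 47% and 39% at 36.

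**The case against.** The strongest reply is that the planned size does give about 80% or more for each combined-versus-single contrast tested alone: 88–91% at 46 per arm, and 79–84% even after the full dropout allowance. That stands. A reader might infer that the trial is too small for these contrasts; the plan's figures do not support that. The loss comes from serial testing, and a different order would give different figures.

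A reader might also take 44–62% as the power at the planned size. It is not. It applies after 20% dropout in every arm, which the plan calls a maximum and Protocol 4.2 expects not to reach. With the plan's example of 5% and 15% dropout by sex (46 × 0.9 ≈ 41 per arm), steps 4 and 5 are at 62–69% and 54–63%. The mixed model also keeps partial data. Even so, steps 4 and 5 stay below 80% with no dropout at all.

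The ANOVA does match the global test, so the calculation is not irrelevant, only incomplete. It would be too strong to say that the sample-size text became outdated only with version 2: SAP 3.1 already mentioned a hierarchical approach in the earlier version, and version 2 spelled out the sequence. Nor is it fair to evaluate the sequence at 19 per arm, since no whole-trial analysis is planned at that size.

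SAP 2.4 can be read more loosely. Ungated, beating UC and at least one single arm has 91–94% power at 36–37 per arm, while beating all three has 68–75%. But SAP 5.2 controls the type I error through the ordered sequence, so the cumulative figures are the ones that govern formal claims. Finally, SAP 3.1 already promises 95% confidence intervals, and nothing says that a stopped sequence will be misread. The reporting sentence proposed below is a safeguard, not the repair of a stated error.

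**Conclusion.** The point holds as a fault in the stated justification, not in the size of the trial. The only printed power belongs to the global test, and its pairing with 19 per group is wrong even there (15 per group for 80%; 91% at 19). That error runs in the cautious direction. No power is stated for the sequence that yields the primary conclusions. For its two combined-versus-single steps the cumulative probability of success is 64–77% at 46 per arm and 44–62% at 36–37 per arm, although each test alone has 79–91%.

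These figures assume absolute-point reductions, zero change under UC, SD 6 and r = 0.8, with change-score or baseline-adjusted residual SDs standing in for the mixed model. If the reductions were meant as relative percentages, the figures would not apply.

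**What to change.** Keep N at about 184. In SAP 2.3 and Protocol 4.2:

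1. Correct the ANOVA statement for f = 0.45 to 15 per group for 80% power, or 19 per group for about 91%. The second option leaves the starting figure for the 46 per arm unchanged. Label it as power for the global test only, and do not present it as the size needed for the primary objective.
2. Add the single-contrast power and the cumulative power by step at both 46 and 36–37 per arm, as tabulated above, with the absolute-points assumption stated beside them.
3. State that a failed or unreached step 4 or 5 will be reported with its estimate and 95% confidence interval, and not as evidence that the combination adds nothing.

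The cost is wording in two documents and no extra participants. The downside is that the stated power for the main comparisons becomes less favourable.

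### The stated 19 per group does not follow from the plan's own inputs, which need 15, and the analyses by sex that justify the sample size are not specified in the current methods

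*SAP*

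**What the plan says.** The current SAP (version 2, section 2.3) and the current Protocol (version 2, section 4.2) give the same calculation. They expect reductions in hepatic fat of 5.0% with TRE + Exercise, 2.5% with TRE, 2.5% with Exercise and no significant change with usual care. They assume an SD of 6 points and a pre-post correlation of 0.8. From these, "we estimate a medium effect size of 0.45". For a one-way ANOVA at alpha 0.05 and power 0.8, the conclusion is that "a minimum of 19 patients per group is required".

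The sections then allow for subgroups by sex and a maximum dropout of 20%: "we will aim to recruit ~46 participants for each trial group", about 184 in total, half of them women. On sex, the SAP says: "Our sample size calculations have taken into account subgroup analyses by sex". It calls the study "adequately powered to detect the specified effect size" even with unequal dropout, and gives an example with 5% dropout in men and 15% in women.

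The current methods treat sex differently. In SAP section 5.2, "sex will be included as a covariate", and Protocol section 4.3 says the same. Neither mentions a separate analysis of men and women, and neither does SAP section 5.4 on additional analyses.

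**The concern.** A sample-size statement should let a reader put in the inputs and get the number out. Here the number is larger than the inputs require, so either an input is misreported or the calculation is wrong, and the documents do not show which.

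The second issue is consistency between current sections. The per-group number was enlarged so that men and women could be analysed separately, yet the methods do not say which outcome, model or test such an analysis would use. A by-sex result could then be produced in several ways, with only the sample-size section to show that something of the kind was intended.

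**Working it through.** **Inputs** (SAP 2.3, repeated in Protocol 4.2): k = 4 equal groups, alpha 0.05, power 0.80, effect size 0.45, expected reductions 5.0, 2.5 and 2.5, SD 6, correlation 0.8, dropout 20%, 46 per arm, half women. Assumptions: 0.45 is Cohen's f, percentages are absolute points, and the usual-care change is 0.

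**1. Trying to reproduce 19.** Power of the ANOVA F test comes from the noncentral F distribution with 3 and 4n − 4 degrees of freedom and noncentrality λ = f² × 4n, where f² = 0.45² = 0.2025.

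| n per group | λ | Power |
|---|---|---|
| 14 | 0.2025 × 56 = 11.34 | 78.4% |
| 15 | 0.2025 × 60 = 12.15 | 81.7% |
| 19 | 0.2025 × 76 = 15.39 | 90.9% |

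The smallest n reaching 80% is 15. The plan's 19 is not reproduced. It is the smallest n for 90% power at f = 0.45, and also the smallest n for 80% power at f = 0.40 (18 gives 79.9%, 19 gives 82.3%). Either reading changes a stated input.

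**2. Starting from the means.** The expected reductions 0, 2.5, 2.5 and 5 have mean 2.5, so the SD of the means is √[(2.5² + 0 + 0 + 2.5²)/4] = √3.125 = 1.768.

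- Change scores: SD = 6 × √(2 × (1 − 0.8)) = 3.795; f = 1.768/3.795 = 0.466; n = 14.
- Baseline-adjusted: SD = 6 × √(1 − 0.8²) = 3.60; f = 1.768/3.60 = 0.491; n = 13.
- Ignoring the correlation: f = 1.768/6 = 0.295; n = 33.

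None of these gives 19.

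**3. What 46 per arm delivers.** At 20% dropout, 46 × 0.8 = 36.8 remain per arm, or 36.8/2 = 18.4 per sex per arm. Power of the global test within one sex at f = 0.45 is 89.8%. In the plan's own example, 23 × 0.85 = 19.55 women per arm give about 92%, and 23 × 0.95 = 21.85 men per arm give about 95%.

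**4. Sex in the current sections, side by side.**

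| Section | Role of sex |
|---|---|
| SAP 2.3, Protocol 4.2 | Subgroup analyses by sex justify N; power claimed for separate analyses |
| SAP 5.2, Protocol 4.3 | Covariate only |
| SAP 5.4 | No by-sex analysis listed |

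A sentence planning all analyses separately for men and women stands only in the superseded methods sections. The mismatch lies within the current text and does not depend on comparison with the old version.

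**The case against.** The strongest defence is that nothing here harms the trial. The stated 19 exceeds the 15 required, and the power claim by sex is tied to the specified effect size, for which it is true. That stands, and it is why the point is minor. It does not make 19 reproducible.

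It can also be said that section 2.3 is dated, prespecified text showing an intention to analyse the sexes separately. That stands too. A reader might infer that any by-sex result would be post hoc; this goes too far. The intention is on record, and what is missing is its specification in the methods.

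Three other stronger readings are tempting:

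- *Recruitment is too small.* Keeping 19 completers per sex would need 2 × 19/0.8 = 47.5 per arm, and 18.4 is below 19. But the gap is 0.6 of a patient, at a dropout described as the maximum, with approximate targets, and against a minimum that is itself too high. The inputs need 15.
- *Dropout is counted twice*, because 15/0.8 = 18.75 rounds to 19. The documents present 19 as the ANOVA minimum and apply dropout afterwards, so this remains a guess.
- *The power claim fails for pairwise comparisons.* SAP 5.2 does go on to these: "If the global test of significance indicates between-group differences, pairwise comparisons will be explored", and "The prespecified hierarchical hypotheses will be tested using the prespecified sequence". But the sample-size sections claim no power for pairwise tests, so their claim cannot be faulted on that ground. It is enough to say which test it covers.

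**Conclusion.** The point holds in two parts, both minor. First, 19 per group does not follow from the stated inputs: f = 0.45 needs 15, the underlying means, SD and correlation need 14 on change scores, and 19 corresponds to about 91% power. The error is in the safe direction, and enrolment is adequate for the global test, including within one sex (about 90% at f = 0.45 and 20% dropout). Second, the by-sex analyses used to justify N are not specified in the current methods.

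The power figures rest on reading 0.45 as Cohen's f, which is reasonable because the test is a one-way ANOVA although the documents do not name the measure. The within-sex figures also assume the same effects, SD and correlation in men and women, since no sex-specific values are given. They are sensitive to the correlation: with f taken from the planned means and 18.4 per sex per arm, a correlation of 0.7 gives 76–84% for the global test (change scores to baseline-adjusted), and 0.9 gives over 99%.

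**What to change.** Enrolment, the main model and the testing sequence stay as they are.

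1. In SAP 2.3 and Protocol 4.2, restate the calculation, for example:

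> Taking the effect size 0.45 as Cohen's f, with four groups and alpha 0.05, 15 participants per group are enough for 80% power and 19 give about 91%. With 46 per arm and 20% dropout, about 37 per arm (about 18 per sex) remain, giving about 90% power for the global test within each sex. Statements about power by sex refer to the global test.

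If the sponsor's records show that 19 came from a different effect size or power, correct that input and recalculate the figures that depend on it.

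2. Align the sections on sex. Either list the by-sex analysis of the primary outcome, with its model, in SAP 5.2 and Protocol 4.3, or state in SAP 2.3 and Protocol 4.2 that separate analyses are no longer planned.

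The cost is a few sentences in two documents. The first option under item 2 specifies an analysis and is more than a wording change, so it should be a dated amendment made before the allocation codes are broken.
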